14.3 Duration of Study

Study duration includes 2 weeks of run-in, followed by 6 weeks of treatment - Total of 8 weeks.

Overall duration of the study is expected to be up to 10 months: up to 8 months of patient enrollment, eight weeks of run-in and treatment period. The goal is to enroll up to 134 subjects.

15. STUDY TREATMENT

Detailed study treatment herein:

15.1 Study Design

The study is a prospective, multicenter, open-label, single-arm pilot study to evaluate the tolerability, efficacy and safety of the Vibrant Capsule in aiding relieving constipation.

The objective is to assess the tolerability, safety and efficacy of the Vibrant Capsule with a frequency of administration of one per day for 2 days, followed by 1 day without. The study is a single-arm study.

The study will be performed in up to 15 centers in the USA.

The study will have one interim analysis.

The interim analysis will be performed after 20 patients complete the study and are evaluable. The following parameters will be assessed: ease of use of the home base unit and the safe use of the new frequency of Vibrant capsule administration.

Depending on the results of the interim analyis:

- The study will be modified to adapt changes for the ease of use or tolerability.
- The study will continue as planned.

Doc No: 220CLD

Rev: 03 Date: August 26, 2016

Page 42 of 93

Data reporting will be done on an electronic Case Report Form (eCRF). In addition, patients will fill in daily information about their bowel movements, clinical symptoms and medication usage on an electronic Diary (eDiary). The eDiary will be accessed via a computer, smartphone, tablet or other suitable device, through a designated website. On smartphone and tablet, the website will be accessed via an application. Information about time of activation of the Vibrant Capsules will be recorded automatically by the base unit and automatically transferred to the eCRF.

Patients with Chronic Idiopathic Constipation (CIC) according to Rome III criteria who failed currently available therapy (defined as osmotic and stimulant laxatives used for at least one month at recommended dose) and meet the inclusion criteria will be offered participation in this study. The background of the proposed study and its risks and benefits will be explained to the patient and the informed consent form will be signed.

Patients will be screened for study eligibility according to inclusion and exclusion criteria. The daily bowel movements frequency, history of constipation, etiology of constipation and medication use (including prescription medication) will be throroughly assessed. Patient demographic and medical information acquired from the patient or the patient's medical chart, including age, gender, previous medical history, risk factors etc. will be also recorded on the eCRF.

In addition, patients will undergo a physical examination including digital rectal examination, vital sign measurements and blood tests.

Patients will then fill in the Rome III questionnaire to confirm the diagnosis of Chronic Idiopathic Constipation and fill out the Bristol Stool Scale. Findings will be recorded on the eCRF.

Eligible patients will then be asked to refrain from taking any medication or supplement they are using to relieve their constipation, and will perform a self-assessment of their normal spontaneous bowel movements for 14 days (run-in period), on the eDiary. Patients will also be asked to record clinical symptoms and usage of any medication or supplement on the eDiary during the run-in period.

After 14 days the patients will visit the medical center for the baseline visit. Eligibility will be re-assessed and confirmed based on the patient's completed eDiary and Rome III questionnaire. The patient will be trained in the medical center to use the base unit. He will activate himself the first capsule and will ingest it in front of the medical staff. All the other capsules will be ingested from the home of the patient. Only the first ingestion will take place in the medical center.

During the treatment period, patients will ingest Vibrant Capsule using the following sequence: one per day for 2 days, 1 day without, one per day for 2 days, 1 day without, etc. The patient will ingest a total of 28 capsules in 6 weeks considering the sequence.

Capsule intake will always be performed at the same time: during the evening, between 9 PM and 10 PM.

Doc No: 220CLD

Rev: 03 Date: August 26, 2016

Page 43 of 93

After 6 weeks, treatment will be ceased and patients will visit the medical center one last time for evaluation and completion of Rome III questionnaire, Bristol Stool Scale and other assessments.

Patients will be instructed to complete a simple patient eDiary throughout the duration of the study. This will include daily recordings of number and time of bowel movements, clinical symptoms and medication/supplements usage, including rescue medication.

Please refer to section 15.15 for a detailed study schedule.

Data collection will include physician identification, investigational device identification data and usage of the capsule. This data will be documented on the eCRF, together with the occurrence of any adverse events during the capsule usage.

All patient adverse events (whether device related or not) will be recorded during the course of the clinical study. All serious adverse events/complications will be reported immediately (within 24 hours) to the study sponsor/monitor and to the Institutional Review Board.

15.2 Medical History

Patient demographic and medical information acquired from the patient or the patient's medical chart, including age, gender, weight, height, body mass index (BMI), number of natural childbirth and previous medical history and medications will be recorded, including: a history of clinically significant abnormalities of all body systems; concurrent diseases; relevant past medical history.

The information will be recorded in the eCRF for all patients participating in this study.

15.3 Constipation History

Full history of constipation will be recorded on the eCRF, including duration of constipation, full history and habits of medication (over the counter and prescription) and supplements use, frequency of spontaneous bowel, current medication/supplements use, usage of rescue medication, description of current diet (with focus on water intake and fiber intake), physical activity (number of hours of physical activity per week), recent change in bowel movements.

15.4 Physical Examination

During the screening visit all patients will undergo a conventional physical examination by an authorized physician. The physical examination will include diagnosis and documentation of any significant abnormalities or diseases.

Doc No: 220CLD

Rev: 03 Date: August 26, 2016

Page 44 of 93

15.5 Assessment of pelvic floor dysfunction (defecatory disorder)

Assessment of pelvic floor dysfunction will be based on patient history. Patients with suspicion of pelvic floor dysfunction will be excluded.

If patients have been previously diagnosed with pelvic floor dysfunction following anorectal manometry, a balloon expulsion test, or other examinations, documented results from these tests can be used to exclude patients.

15.6 Blood and urine tests

During the screening visit all patients will undergo the following blood tests: blood count, calcium, creatinine, Blood Urea Nitrogen (BUN), sodium, potassium and TSH. Blood pregnancy test will be performed during the screening visit. A pregnancy urine test will be performed during the baseline visit.

15.7 Screening visit (day -14)

At the screening visit, subjects will be evaluated for eligibility and undergo physical examination, digital rectal examination, vital sign measurements and blood tests. They will undergo a thorough interview about their constipation and the Rome III questionnaire (see appendix C) will be completed. The Bristol Stool Scale (see Appendix A) will also be completed by the patient.

The investigator will confirm their eligibility and their physical and mental suitability to participate in this study.

Patients exiting the trial at this stage will be considered screening failure patients and be replaced with new patients to reach the goal of 120 patients.

The patient will be trained by the study coordinator to access and use the eDiary. The eDiary contains questions about bowel movements and their associated clinical symptoms (straining, abdominal pain, abdominal discomfort, abdominal gas, bloating, abdominal pain during defecation, need for digital maneuver, sensation of complete evacuation), usage of rescue medication and usage of other medication or supplements (name of drug, dosage, number of takes per day, reason for medication). The information will be transferred to the eCRF every day.

The patient will define his/her preferred device to use the eDiary. The patient and study coordinator will define together the time of the day during which the patient will fill in the eDiary and a daily alert will be set up on the phone of the patient. The daily diary can be found in Appendix D.

Doc No: 220CLD

Rev: 03 Date: August 26, 2016

Page 45 of 93

15.8 Run-in period (day -14 to -1)

Eligible patients will be observed and monitored for the first 2 weeks, in which they will be asked to refrain from taking any medication or supplement to relieve their constipation.

Patients will complete the eDiary every day.

The patients will receive 2 short phone calls/week from the study coordinator. The phone calls will be about 5-10 minutes long and will ask check patient compliance with the eDiary, occurrence of adverse events, use of rescue medication, patient understanding of what he needs to do in the context of the study and discuss any issue or difficulty that the patient might have. The phone calls will be made more than 1 day apart. Confirmation of date and time of the phone call will be reported on the eCRF.

If a patient does not fill in his/her eDiary, the sponsor/investigator will be alerted and the patient will be contacted by phone call the next day in order to receive more information and gather the missing information. Compliance of the patient will be closely monitored.

15.9 Treatment

On day 0 (baseline visit), the patient will arrive to the clinic. Eligibility will be reassessed and confirmed based on the Rome III questionnaire and on the patient's completed diary. Based on the Vibrant Capsule's intended use, patients need to have an average of at least 1 SBM per week but less than 3 SBM per week during the two weeks of run-in.

The Bristol Stool Scale will be completed.

Eligible patients will take the Vibrant Capsules. The study is open-label.

Treatment duration is 6 weeks.

The patient will be trained by the study coordinator to activate the Vibrant Capsules using the base unit. After an oral explanation, the patient will read the label, and the study coordinator will make sure the patient fully understands how to use the base unit. The patient will then activate his/her first capsule, in front of the study coordinator, and swallow it.

The patient will be released home with the base unit and capsules for the first three weeks of treatment. He/She will be asked to continue with the daily completion of the eDiary. Actual point of enrollment for the patient is considered the day of first capsule intake.

Patients will be asked to refrain from any medication or supplement they are using to relieve their constipation, throughout the treatment period. A rescue treatment will be authorized upon need (refer to section 15.10 for details).

Capsule intake will be performed during the evening between 9 PM and 10 PM. Only the first intake, which is in the medical center, will not take place at such a time.

Doc No: 220CLD

Rev: 03 Date: August 26, 2016

Page 46 of 93

Half of the capsules the patient is scheduled to take will be provided at the baseline visit. The patient will be provided with the second half of the capsules during a mid-treatment visit to the medical center (day 21).

The first week of treatment, the patient will receive two short phone calls from the study coordinator. Starting the second week of treatment, he will receive one phone call per week.

The phone calls will be about 5-10 minutes long and will check patient compliance with capsule ingestion and the eDiary, occurrence of adverse events, use of rescue medication, patient understanding of what he/she needs to do in the context of the study and discuss any issue or difficulty that the patient might have. During the week when two phone calls are needed, the phone calls will be made more than 1 day apart. Confirmation of date and time of the phone call will be reported on the eCRF.

If a patient does not fill in his eDiary, the investigator will be alerted and the patient will be contacted by phone call the next day in order to receive more information and gather the missing information. Compliance of the patient will be closely monitored.

After three weeks of treatment, the patient will come back to the medical center. An interview will be conducted, where the following topics will be discussed: occurrence of adverse events, compliance to filling in the daily information on the eDiary, concomitant medication/rescue taken, evolution of constipation symptoms, patient's perceptions about the treatment, motivation of the patient, or any other topic relevant. The patient will bring back all remaining capsules (spare not activated and defective) from the first 3 weeks of treatment.

The patient will receive capsules for the last three weeks of the treatment period and will be released home.

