Rev: 03 Date: August 26, 2016

Page 7 of 93

3. List of Abbreviations

% Percent

AE Adverse Event

ADE Adverse Device Effect

AGA American Gastroenterological Association

AR Authorized Representative

BMI Body Mass Index BUN Blood Urea Nitrogen

CSBM Complete Spontaneous Bowel Movement

eCRF Electronic Case Report Form

CI Confidence Interval

CIC Chronic Idiopathic Constipation

EC Ethics Committee
ECG Electrocardiogram
EDC Electronic Data Capture
FA Full Analysis Set

FC Functional Constipation GCP Good Clinical Practice

FDA Food and Drug Administration

IBS-C Irritable Bowel Syndrome with Constipation

ICF Informed Consent Form

ICH International Conference on Harmonization of Technical Requirements for

Registration of Pharmaceuticals for Human Use

IFU Instruction for Use

IRB Institutional Review Board ISF Investigator Site Files

Mg Milligram
μg Microgram
Min minute(s)
MFR Manufacturer

NCAs National Competent Authorities

NSAIDs Non-Steroidal Anti-Inflammatory Drugs

OTC Over The Counter
PEG Polyethylene glycol
PI Principal Investigator

PP Per Protocol QOL Quality of life

SAE Serious Adverse Event

SADE Serious Adverse Device Effect SBM Spontaneous Bowel Movement

US United States

USADE Unanticipated Serious Adverse Device Effect

Doc No: 220CLD

Rev: 03 Date: August 26, 2016

Page 8 of 93

4. Protocol Synopsis

Name	A prospective, multicenter, open-label, single-arm study to assess the tolerability, safety and efficacy of a new frequency of Vibrant Capsule administration
Indication	The Vibrant Capsule is intended for the treatment of patients with Functional Constipation, with an average of ≥1 and <2.5 spontaneous bowel movements (SBMs) per week
Objectives	The objectives are to assess the tolerability, safety and efficacy of a new frequency of Vibrant Capsule administration: one per day for 2 days, followed by one day without
Design	The study is a prospective, multicenter, open-label, single-arm study, to evaluate the tolerability, safety and efficacy of the Vibrant Capsule in relieving constipation.
	One arm will be assessed: Vibrant Capsule administered with a sequence of one per day for 2 days, followed by one day without, one per day for 2 days followed by one day without, etc. (14 capsules in 3 weeks).
	The study will be performed in up to 15 centers in the USA.

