Inclusion criteria	 Patients aged 22 years and older Patients with Chronic Idiopathic Constipation (CIC) according to Rome III criteria and who have not experienced relief of their symptoms from available therapies (osmotic and stimulant laxatives used for at least one month at recommended dose) Patients with an average of <3 Spontaneous Bowel Movements (SBM) per week and ≥1 SBM per week Normal colonoscopy performed within 10 years prior to study participation, unless the patients are <50 years old and without alarm signs and/or symptoms Patient signed the Informed Consent Form (ICF) Female subjects must have a negative urine pregnancy test and must not be lactating prior to receiving study medication. For females of child-bearing potential, a hormonal (i.e., oral, implantable, or injectable) and single-barrier method, or a double-barrier method of birth control must be used throughout the study. All other female subjects must have the reason for their inability to bear children documented in the medical record [i.e., tubal ligation, hysterectomy, or post-menopausal (defined as a minimum of one year since the last menstrual period)]; in these circumstances, a urine pregnancy test will not be necessary.
Exclusion criteria	 History of complicated/obstructive diverticular disease History of intestinal or colonic obstruction, or suspected intestinal obstruction. History of significant gastrointestinal disorder, including any form of inflammatory bowel disease or gastrointestinal malignancy (celiac disease is accepted if the subject has been treated and is in remission) History of gastroparesis Use of any of the following medications: Medications that may affect intestinal motility, prokinetics, anti-depressants, anti-Parkinsonian medications, opiates, opioids, calcium-channel blockers, aluminum/magnesium hydroxide With the exception of antidepressants, thyroid or hormonal replacement therapy, when the subject has been on a stable dose for at least 3 months prior to enrollment. Clinical evidence of significant respiratory, cardiovascular, renal, hepatic, biliary, endocrine, psychiatric or neurologic disease. Presence of cardiac pacemaker or gastric electrical stimulator. History of, or current eating disorders, such as anorexia, bulimia, or compulsory overeating.

Doc No: 220CLD

Rev: 03 Date: August 26, 2016

Page 11 of 93

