7.2 Intended Use

The Vibrant Capsule is intended to for the relief of patients with Functional Constipation (FC), with an average of at least 1 and less than 2.5 spontaneous bowel movements (SBMs) per week.

Doc No: 220CLD

Rev: 03 Date: August 26, 2016

[figure not shown]
Page 15 of 93

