14.1 Inclusion Criteria

- 1. Patients aged 22 years and older
- 2. Patients with Chronic Idiopathic Constipation (CIC) according to Rome III criteria and who have not experienced relief of their symptoms from available therapies (osmotic and stimulant laxatives used for at least one month at recommended dose)
- 3. Patients with an average of <3 Spontaneous Bowel Movements (SBM) per week and ≥1 SBM per week

Doc No: 220CLD

Rev: 03 Date: August 26, 2016

Page 40 of 93

4. Normal colonoscopy performed within 10 years prior to study participation, unless the patients are <50 years old and without alarm signs and/or symptoms

- 5. Patient signed the Informed Consent Form (ICF)
- 6. Female subjects must have a negative urine pregnancy test and must not be lactating prior to receiving study medication. For females of child-bearing potential, a hormonal (i.e., oral, implantable, or injectable) and single-barrier method, or a double-barrier method of birth control must be used throughout the study. All other female subjects must have the reason for their inability to bear children documented in the medical record [i.e., tubal ligation, hysterectomy, or post-menopausal (defined as a minimum of one year since the last menstrual period)]; in these circumstances, a urine pregnancy test will not be necessary.

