17.7.2 Per-Protocol (PP)

The per-protocol analysis set will consist of all subjects from the FA analysis set without major protocol violations.

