17.7.3 Statistical Analysis of Analysis Sets

The FA analysis set will serve as the main set for safety assessments.

The PP analysis set will serve as the main set for efficacy assessments.

The primary efficacy assessment will also be performed on the FA analysis set.

Doc No: 220CLD

Rev: 03 Date: August 26, 2016

Page 57 of 93

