17.8.5 Efficacy Analysis

The subject's success status (i.e. if the subjects achieve an increase from baseline of at least 1 weekly SBM during at least 3 out of the 6 treatment weeks) will be calculated. The success rate will be presented along with its exact binomial two sided 95% Confidence Intervals (CI).

Ease of Use will be presented in a tabular form.

Doc No: 220CLD

Rev: 03 Date: August 26, 2016

Page 58 of 93

The CSBM success rate will be analyzed in the same manner.

The change from baseline in number of weekly SBM will be modeled with an Analysis of Covariance (ANCOVA) model, with baseline weekly number of SBM and site as covariates. The adjusted means of the change from baseline will be presented along with its 95% CI.

The change from baseline in count of weekly CSBM, and in symptoms, will be analyzed with similar ANCOVA models, with their respective baseline values as covariate.

Time to occurrence of SBM after intake of the first Vibrant capsule will be assessed and presented by Kaplan-Meier curves.

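### Section 15.9 attributes an entry limit of fewer than 3 SBMs per week to the intended use, which is stated as fewer than 2.5; no success rate is planned for the stated indication

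*Combined protocol and SAP*

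**What the plan says.** The documents give two upper limits for the baseline SBM average.

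- **Below 2.5.** The Indication row of the synopsis describes patients "with an average of ≥1 and <2.5 spontaneous bowel movements (SBMs) per week". Section 7.2 (Intended Use) repeats the range: "with an average of at least 1 and less than 2.5 spontaneous bowel movements (SBMs) per week".
- **Below 3.** Criterion 3 in the synopsis reads "Patients with an average of <3 Spontaneous Bowel Movements (SBM) per week and ≥1 SBM per week", and section 14.1 has the same criterion. Section 15.9, on the eligibility recheck at the baseline visit, says that on the basis of the device's "intended use, patients need to have an average of at least 1 SBM per week but less than 3 SBM per week".

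The primary endpoint (13.1 and 17.2.1) is the proportion of subjects who gain at least one weekly SBM over run-in in at least 3 of 6 treatment weeks, with no restriction on baseline SBM. Section 17.7.2 defines the per-protocol set as "all subjects from the FA analysis set without major protocol violations", and 17.7.3 adds: "The PP analysis set will serve as the main set for efficacy assessments". Section 17.8.5 plans one success rate with an exact 95% interval. Baseline SBM appears only as a covariate, in the ANCOVA for change in weekly SBM (17.8.5) and in the logistic poolability model (17.8.6).

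**The concern.** Section 15.9 names the intended use as its source and then gives a limit that the intended-use section does not contain. The effect goes beyond wording. A subject who averages 2.5 SBMs per week meets criterion 3, so that value alone is no protocol violation. The subject stays in the main efficacy set and counts in the headline rate, yet lies outside the indication in the synopsis and 7.2.

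The study tests no hypothesis on its primary endpoint. Its product is an estimate, and an estimate needs a named population. As planned, the estimate mixes subjects inside the indication with an unreported number outside it, and a reader cannot recover the rate for the indication itself.

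**Working it through.** **The plan's own figure.** Section 17.4 gives 120 completers and 10% dropout: 120 / (1 - 0.10) = 133.3, rounded up to 134. This reproduces, and the concern does not change it. The calculations below use 120.

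**Who is in the gap.** The run-in is 14 days (15.1), so with a complete diary the weekly average is the total divided by 2.

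| SBMs in 14 days | Weekly average | Below 3 | Below 2.5 | Weekly count needed for a gain of at least 1 |
|---|---|---|---|---|
| 2 | 1.0 | yes | yes | 2 |
| 3 | 1.5 | yes | yes | 3 |
| 4 | 2.0 | yes | yes | 3 |
| 5 | 2.5 | yes | no | 4 |

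The gap is the single value of 5 SBMs. Incomplete diaries could give other averages if prorated, for example 7 x 5 / 13 = 2.69, but the visible text has no proration rule. The last column follows because weekly counts are whole numbers. The group outside the indication faces the highest threshold for success.

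**How large the group might be.** The documents give no baseline distribution, so this is an assumption: 14-day totals are Poisson with mean twice the weekly mean, kept only if the total is 2 to 5. The share is P(5) / [P(2) + P(3) + P(4) + P(5)]. At a weekly mean of 1.0 the 14-day mean is 2, and after cancelling the common factor the four terms are 2.000, 1.333, 0.667 and 0.267. The share is 0.267 / 4.267 = 0.063.

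| Weekly mean | 1.0 | 1.25 | 1.5 | 1.75 | 2.0 | 2.25 | 2.5 |
|---|---|---|---|---|---|---|---|
| Share with 5 SBMs | 6% | 10% | 14% | 18% | 23% | 27% | 31% |

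Of 120 subjects this is about 8 to 37, which leaves 112 to 83 inside the indication.

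**How far the rate might move.** The rate below 2.5 minus the overall rate equals the share times the difference in success between the two groups. To put values on this, subjects' weekly SBM rates were drawn from a gamma distribution (shape 1, 2, 4 or 8; mean 1.5 to 2.5 in steps of 0.25). The run-in total was Poisson and kept if 2 to 5. Six weekly treatment counts were Poisson at 1.0, 1.5 or 2.0 times the subject's own rate. That makes 4 x 5 x 3 = 60 scenarios, each with 2,000,000 simulated subjects before the eligibility cut. The share at 5 SBMs was 15 to 26%.

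| Assumed effect on SBM rate | Success rate below 2.5 minus overall rate |
|---|---|
| none | +1.3 to +7.1 points |
| 1.5-fold | +0.2 to +5.3 points |
| 2-fold | -0.6 to +3.5 points |

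In one scenario (mean 1.75, shape 4, no effect) the rate is 27.8% overall and 31.1% below 2.5. By run-in total of 2, 3, 4 and 5 it is 44, 20, 28 and 12%.

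**Scale.** The exact 95% interval at 60/120 is 40.7 to 59.3%, a half-width of 9.3 points. Every simulated shift is smaller than that.

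**Is the rate reported anywhere?** The list in 17.2.2 and the analyses in 17.7 and 17.8 contain no success rate for subjects below 2.5 and no count at or above it. The secondary-endpoint lists in the synopsis and 13.2 are blank in the public text and are not relied on here. The baseline tabulation in 17.8.3 includes a maximum, which could show whether anyone reached 2.5 but not how many.

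**The case against.** The entry rule is not ambiguous. Criterion 3 and the baseline recheck agree on below 3, so no site would enrol differently and no analyst would build a different set. A study may enrol more widely than an intended-use statement, and the device and prior-study sections, which are blacked out, may explain either limit. On this view the only certain error is one attribution in 15.9. The gap is essentially one boundary value, its size is assumed throughout, and the likely shift is below sampling error. Baseline SBM is already modelled. The simulated example also shows success varying from 20 to 44% within the below-2.5 range, so a cut at 2.5 does not isolate a homogeneous group.

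Much of this stands. The size is modest and rests on assumptions, the direction is not certain, and the below-2.5 group is itself a mixture. A table by run-in total would be more informative than a single cut. But the visible sections still contradict one another, and no blacked-out rationale can make 7.2 and 15.9 agree. A covariate in a poolability model or an ANCOVA does not give a success rate for the indication. The supportive rate is wanted because the documents name that range as the population for the device, and no claim of a break in response at 2.5 is needed.

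**Conclusion.** The concern holds. Section 15.9 misstates the intended use given in 7.2, and the primary success rate covers a wider population than the stated indication without reporting how much wider. With complete diaries the excess is exactly the subjects with 5 run-in SBMs. Under the Poisson assumptions they are 6 to 31% of subjects, and across the 60 simulated scenarios the rate within the indication differs from the reported rate by -0.6 to +7.1 points. The largest shifts arise when the device has no effect. These sizes depend on assumed SBM distributions, because the documents supply none; the contradiction does not. It should be corrected, but it does not undermine the study.

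**What to change.** Reconcile the SBM range across the synopsis indication, 7.2, criterion 3 in the synopsis and in 14.1, and 15.9. This review does not say which limit is right. If a single range results, nothing more is needed. If both limits are kept on purpose:

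- correct 15.9 so that it no longer attributes the limit of 3 to the intended use;
- report the number of subjects with a run-in average of 2.5 or more;
- add to 17.8.5: *As a supportive presentation, alongside the primary result, the SBM success rate with its exact two-sided 95% confidence interval will be shown for subjects whose run-in average is at least 1 and below 2.5 SBMs per week.*

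The cost is wording in up to five places, one count and one table from diary data already collected. Eligibility, sample size and the primary analysis can stay as they are. The drawback is a less precise subset estimate: at about 50% success the half-width is 9.6 points with 112 subjects and 11.2 with 83, against 9.3 with 120.
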